3.2 Exclusion Criteria

Prospective participants who meet any of the following criteria will not be eligible for admission into the study:

Concomitant medications

- ___ 1. Current or planned use of other investigational agents, or concurrent biological, chemotherapy, or radiation therapy during the study treatment period. (See inclusion criterion #7 for washout times).
- ___ 2. Current or planned growth factor or transfusion support. If growth factor or transfusion support is provided between screening and start of treatment, the participant will no longer be eligible.

Other illnesses or conditions

- ___ 3. Prior Allogeneic transplant.
- ___ 4. Acute active infection requiring systemic therapy within 2 weeks prior to enrollment.
- ___ 5. Known history of hepatitis B or hepatitis C infection
- ___ 6. Known HIV infection.
- ___ 7. History of allergic reactions attributed to compounds of similar chemical or biologic composition to leflunomide or cholestyramine.
- ___ 8. Non-hematologic malignancy within the past 3 years aside from the following exceptions:
 - adequately treated basal cell or squamous cell skin cancer
 - carcinoma in situ of the cervix
 - prostate cancer < Gleason Grade 6 with a stable PSA
 - successfully treated in situ carcinoma of the breast

___9. Clinically significant medical disease or condition that, in the investigator's opinion, may interfere with protocol adherence or the patient's ability to give informed consent.

___10. Pregnant women and women who are lactating. Leflunomide has potential for teratogenic or abortifacient effects. Because there is a potential risk for adverse events in nursing infants secondary to treatment of the mother with these agents, breastfeeding should be discontinued if the mother is enrolled on this study.

___11. Any other condition that would, in the Investigator's judgment, contraindicate the patient's participation in the clinical study due to safety concerns or compliance with clinical study procedures, e.g., infection/inflammation, intestinal obstruction, unable to swallow medication, social/ psychological issues, etc.

Noncompliance

___12. Prospective participants who, in the opinion of the investigator, may not be able to comply with all study procedures (including compliance issues related to feasibility/logistics).

Eligibility Confirmed* by (Choose as applicable):	Print Name	Signature	Date
 Site PI			
 Authorized study MD			
 Study Nurse			
 Study CRA/ CRC			
 _____			
Other: _____			

*Eligibility should be confirmed per institutional policies.

3.3 Inclusion of Women and Minorities

The study is open anyone regardless of gender or race/ethnicity. Efforts will be made to extend the accrual to a representative population. However, a balance must be struck between subject safety considerations and limitations on the number of individuals exposed to potentially toxic or ineffective treatments on the one hand and the need to explore gender, racial, and ethnic aspects of clinical research on the other. If differences in outcome that correlate to gender, racial, or ethnic identity are noted, accrual may be expanded or additional studies may be performed to investigate those differences more fully.

4.0 PARTICIPANT ENROLLMENT

4.1 Pre-Enrollment Informed Consent and Screening Procedures

Diagnostic or laboratory studies performed exclusively to determine eligibility will be done only after obtaining written informed consent. Studies or procedures that are performed for clinical indications (not exclusively to determine study eligibility) may be used for baseline values and/or to determine pre-eligibility, even if the studies were done before informed consent was obtained. The informed consent process is to be fully documented (see Section 17.4), and the prospective participant must receive a copy of the signed informed consent document. Screening procedures are listed in Section 10.0 (Study Calendar).

4.2.2 Slot verification and reservation

Designated study staff should call or email the DCC to verify current slot availability, and to reserve a slot for a specific prospective subject (provide DCC with subject initials). Slots can only be held for a limited time.

The DCC should be notified of cancellations of prospective participants holding slots as soon as possible.

4.2.3 Registration Process

To register a participant the subsequent procedure is to be followed:

1. The study team (data manager/coordinator/research nurse) should contact the DCC via telephone or email to provide notification regarding the pending registration and communicate desired timeline of the registration, especially if it must be completed promptly to meet the registration window.
2. The data manager/coordinator/research nurse will email a copy of the following documents to the DCC:
 - Completed eligibility checklist (printed from [Section 3.0](#) of the protocol)
 - Source documentation to support eligibility criteria**
 - Signed Informed Consent
 - Signed subject's bill of Rights
 - Signed HIPAA authorization form (if separate from informed consent)

** It is **NOT** acceptable to submit emails as source documentation
3. After having received all transferred documentation, the DCC will complete the review of the documents to verify eligibility, working with the study team as needed to resolve any missing required source elements. A participant failing to meet all protocol eligibility requirements will not be registered.
4. Once eligibility is confirmed, DCC staff will send a Confirmation of Registration Form and signed Eligibility Checklist within 24 hours, including the participant study number and cohort assignment (dose level or expansion cohort) to:
 - The study team: Principal Investigator, treating physician, protocol statistician, protocol nurse, CRC and COH IDS Pharmacy.
 - the COH sponsor team designees, including Study PI

5. Upon receipt of the Confirmation of Registration email from the DCC, COH study team will register the patient in OnCore.

4.3 Screen Failures and Registered Participants Who Do Not begin Study Treatment

Notify the DCC if the participant screen fails after registration or if the participant does not start treatment.

Issues that would cause treatment delays should be discussed with the Principal Investigator.

5.0 TREATMENT PROGRAM

5.1 Treatment Program Overview

Treatment on study will be in the outpatient setting and will consist of daily treatment with leflunomide; patients will be treated in planned 28-day treatment cycles for up to 13 cycles (approximately 1 year) until meeting any off-protocol treatment criteria ([Section 5.6](#)). After the decision to end study treatment has been made, participants will receive treatment with cholestyramine ([Section 5.5](#)) to eliminate leflunomide. Participants who end study treatment for reasons other than disease progression will undergo active follow-up ([Section 5.7](#)) until disease progression or 12 months of active follow-up, whichever is earlier. For a detailed tabular view of the treatment, monitoring, and follow-up schedule, see the Study Calendar in [Section 10.0](#).

5.2 Cycle Definition

The planned cycle length is 28 days. Leflunomide will be taken orally once daily. Missed or held doses will not be made up. The day count continues despite a hold in agent administration. Day 1 safety assessments must be reviewed prior to the initiation of the cycle. **For a cycle to commence, the participant must be actively taking study agent.** Windows for procedures are detailed in [Section 10.0](#).

5.3 Agent Administration

5.3.1 Leflunomide

Participants will be instructed to take each dose of leflunomide orally, once a day, at approximately the same time each day. They may take it with or without food. If a patient forgets or misses a dose for whatever reason, it should not be replaced or made up. Participants will be given a study calendar (pill diary, see [Appendix D](#)) to document each dose of leflunomide that is taken or missed.

Leflunomide is administered with a loading dose of 100 mg/day for the first three doses (first three days) in Cycle 1. Starting day 4 in Cycle 1 and for all later cycles, it will be administered at 20 mg/day (or 10 mg/day if dose reduced due to toxicities).

There will be no intra-patient dose escalation; patients will undergo dose modification due to toxicity per [Section 7.2](#).

5.3.2 Cholestyramine

Cholestyramine is not a study agent but is required for the elimination of the study agent leflunomide. See [Section 5.5](#) for cholestyramine administration details.

5.4 Assessments and Special Monitoring

For a detailed list of all study procedures including timing and windows, see [Section 10.0](#).

5.5 End of Treatment Evaluations and Leflunomide Detoxification

All participants will be followed until resolution or stabilization of any serious adverse events occurring during treatment and completion of the Day 30 End of Treatment assessments. See [Section 10](#) for a list of all assessments and windows.

Because of the ability of leflunomide to be reabsorbed through the colon, resulting in a very long half-life, all participants will be treated with cholestyramine to prevent re-absorption of leflunomide after the decision to end study treatment has been made.

Participants removed from study treatment will undergo oral administration of cholestyramine 8 grams oral suspension three times daily for 11 days. It will not be a deviation if an administration of cholestyramine is delayed or if the 11 days are not consecutive. Cholestyramine administration may be adjusted per the discretion of the treating investigator. After the treatment with cholestyramine, clinical laboratory testing will be performed to verify plasma levels less than 0.02 mg/L or 0.02 μ g/mL by two separate tests at least 14 days apart. If plasma levels are higher than 0.02 mg/L or 0.02 μ g/mL, additional cholestyramine treatment will be considered. See Section 10 for a tabular view of cholestyramine administration and metabolite testing windows and days of administration.

Note: Cholestyramine can affect the absorption of other oral medications. Such medications should be taken 1 hour before administration of cholestyramine on any day or per other guidance in the package insert. Watch for bleeding abnormalities due to vitamin K deficiency for which intravenous vitamin K may be administered.

5.6 Duration of Therapy and Criteria for Removal from Protocol Therapy

Patients will receive study treatment for a maximum of 13 cycles until disease progression, unacceptable toxicity or other criteria for removal from study treatment are satisfied. Participants may be removed from treatment for any of the following reasons:

- Evidence of disease progression per mSWAT (see [Appendix C](#))
- Participant receives 13 cycles (~ 12 months of protocol therapy)
- Patient is deemed intolerant to study treatment because of toxicity, despite dose modification/delay
- Participant withdraws from the treatment phase of the study
- General or specific changes in the participant's condition, including non-compliance, which renders the participant unacceptable for further treatment in the opinion of the treating investigator.

Documentation of the reason for discontinuing therapy and the date effective should be made in the medical record and appropriate eCRF. The participant should then proceed to off-treatment procedures for safety monitoring, leflunomide elimination and follow-up procedures. The participant's status is to be modified in the OnCore system once the off-treatment period is completed. Alternative care options will be discussed with the participant.

5.7 Active Follow-Up

Participants who do not progress while on treatment (regardless of whether the patient finished 13 cycles or terminated treatment early) will be in *Active Follow Up*, for 12 months after the end of the protocol treatment, where they will continue to undergo response assessment every 3 months, until disease progression or otherwise meeting an criteria for removal from study participation as detailed in Section 5.8.

The schedule and windows for assessments and data collection points are further detailed in Table 10.

Assessment time points and windows are detailed in [Section 10.0](#).

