5.8 Duration of Study Participation

Participants may be removed from the study as a whole at any time at their own request, or they may be withdrawn at the discretion of the investigator for safety, behavioral or administrative reasons. The reason(s) for discontinuing study participation should be documented and may include:

- Completion of 12 months of active follow up after the end of protocol treatment
- Disease progression per mSWAT, after completing the End of Treatment assessments
- Disease progression per mSWAT during active follow-up
- Withdrawal of consent
- Participant is lost to follow-up. All attempts to contact the participant must be documented.
- At the discretion of the investigator for safety, behavioral, study termination or administrative reasons

Documentation of the reason for discontinuing study participation and the date effective should be made in the Electronic Health Record/medical record and appropriate eCRF

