5.9 Prohibited and Concomitant Therapies/Medications

5.9.1 Allowed concomitant medications

Concomitant medications and treatments that are permitted while on study treatment include allopurinol, anti-emetics, anti-diarrheals, FDA-approved bisphosphonates, erythropoietin, transfusions (as necessary), and palliative radiation.

Concurrent treatment with any other anti-neoplastic therapies will not be permitted while on study treatment. Concurrent administration of live vaccines will not be permitted while on study treatment.

During cycle 1 only: Transfusions are not permitted unless platelets <25,000/mm³ or platelets < 50,000/ mm³ accompanied by bleeding. Growth factors are not permitted unless ANC <500/ mm³.

If concomitant therapy must be added or changed, including over-the-counter medications or alternative therapies, the reason and name of the agent/therapy should be recorded in the eCRF and documented in the Electronic Health Record/medical record.

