10.0 STUDY CALENDAR

Table 10 describes required procedures. All procedures may increase in frequency if clinically indicated or oriented following toxicity. Adjustments to the treatment cycle due to a hold in study agent are detailed in [Section 5.2](#).

Table 10.0 Study Activity Calendar

	Screen -ing ^a	Cycle 1, 2, 3		Cycle 4+ Day 1 ^d	End of Treatment ^e				Active Follow-Up ^j
		Day 1 ^b	Day 14 ^c		Day 0 ^f	Days 1-11 ^g	Day 14 ^h	Day 30 ⁱ	
Informed Consent ^k	X ^s								
Inclusion/Exclusion Criteria ^l	X								
Registration ^m	X ⁿ								
Medical history ⁿ	X								
Physical exam	X	X		X				X	
Vital signs ^o	X	X		X				X	
Adverse events assessment ^p		X	X	X	X	X		X	
Concomitant meds review	X	X		X	X			X	
ECOG status (Appendix A) ^q	X	X		X				X	
Pregnancy test ^q	X								
TB antigen test ^r	X								
Hepatitis A, B, C testing	X ^s								
Skin photographs ^t	X	X		X	X			X	X
mSWAT ^u	X	X		X	X			X	X
Skin biopsy ^v		X ^w		X ^w				X ^w	
CBC with differential ^x	X	X	X	X				X	X
Chemistry panel ^y	X	X	X	X				X	X
Response assessment ^z		X		X	X			X	X
Teriflunomide clinical testing ^{aa}				X			X ^{dd}	X ^{dd}	
Leflunomide administration ^{bb}		Daily							
Cholestyramine ^g						X ^g			

- a. All screening procedures to be performed within 21 days of start of study agent except informed consent, acute hepatitis panel, skeletal survey which may occur within 30 days of start of treatment (footnote u) and except for registration which must occur within 7 days from start of treatment (footnote n).
- b. Day 1 assessments to be performed within 5 days (120 hours) prior to Day 1 drug (except footnote u for C1 only). Day 1 safety assessments must be resulted and reviewed prior to administration of agent for the cycle that is initiating. Screening assessments, if performed within this aforementioned time frame, may serve as C1D1 assessments. Note: items with footnote "aa" are not performed for C1D1; the windows for screening assessments still apply.
- c. Day 14 evaluations have +/- 3 day window.
- d. Day 1 assessments to be performed within 5 days (120 hours) prior to Day 1 drug. Day 1 safety assessments must be resulted and reviewed prior to administration of agent for the cycle that is initiating.
- e. Reasons to end study treatment include disease progression and unacceptable toxicity. See Section 5.8 for all criteria.

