11.2 Efficacy Endpoints

Response on this study will be assessed by mSWAT (see Appendix C). In addition to mSWAT, individual lesions will also be assessed by the Composite Assessment of Index Lesion Severity (CAILS) tool (see [Appendix E](#)).

Overall Response Rate:

- Defined as the proportion of patients with a documented response (CR or PR) any time during study treatment.

Complete Response Rate:

- Defined as the proportion of patients with a documented CR any time during study treatment.

Duration of response:

- Defined as the time interval from the date of first documented response (CR or PR) to the first documented disease progression or death, whichever occurs first. Patients without a documented CR or PR will be excluded. Patients who do not achieve CR or PR are excluded from this analysis.

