14.3 Expedited Reporting

The table below indicates what events to report to expeditiously (Table 14.3).

Table 14.3 Expedited Reporting Guidelines

Time point	What to report
From signing of the consent to study completion	
• All UPs and AEs that meet the definition of a UP
For the time period beginning at treatment through 90 days following cessation of treatment, or 30 days following cessation of treatment if the subject initiates new anticancer therapy, whichever is earlier	
• All SAEs regardless of relationship to protocol therapy• All AESIs, overdose• AESIs (Section 14.2)- irAEs, overdose

All reportable events will require follow up until stabilization or resolution per the agreement of the Study PI.	
From Day 1 of protocol therapy up to 90 days post-last leflunomide dose	
• Pregnancies and lactation
Post Safety follow-up to removal from study	
• All SAEs that are at least possibly related to leflunomide.
NOTE: All events reported expeditiously require follow-up reporting until the event is resolved, stabilized, or determined to be irreversible by the investigator.	

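### Duration of response has no rule for lymphoma therapy started before progression, and Active Follow-Up schedules no collection of it, so disease control on a later therapy can count as leflunomide's

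*Combined protocol and SAP*

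**What the plan says.** Section 5.7 (Active Follow-Up) covers "Participants who do not progress while on treatment (regardless of whether the patient finished 13 cycles or terminated treatment early". For 12 months after treatment "they will continue to undergo response assessment every 3 months, until disease progression or otherwise meeting an criteria for removal from study participation". The removal reasons in Section 5.8 include "Disease progression per mSWAT during active follow-up", but not the start of another lymphoma therapy. That list is worded as examples and has an investigator-discretion item.

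Section 5.9.1 limits other therapy only during treatment: "Concurrent treatment with any other anti-neoplastic therapies will not be permitted while on study treatment". Section 5.6 adds that, when treatment stops, "Alternative care options will be discussed with the participant".

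Section 11.2 defines DOR as "the time interval from the date of first documented response (CR or PR) to the first documented disease progression or death". Section 12.4 names the Kaplan-Meier estimator and a median where estimable, and says nothing about censoring.

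In Table 10.0 the row "Concomitant meds review" is marked at screening, at Day 1 of the cycles, and at End of Treatment Day 0 and Day 30. Its Active Follow-Up cell is empty, while photographs, mSWAT, blood count, chemistry and response assessment are marked there. New anticancer therapy is mentioned in Table 14.3, where the safety-reporting window can close "30 days following cessation of treatment if the subject initiates new anticancer therapy".

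**The concern.** Duration of response to leflunomide is a secondary objective (Section 1.2). Leflunomide stops after at most 13 cycles, or earlier for toxicity, and is then washed out with cholestyramine. A responder can therefore be followed for up to a year off the drug, free to start something else. Section 2.1 names therapies in use for these diseases: phototherapy, methotrexate, bexarotene and brentuximab vedotin.

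If such a patient starts one before progressing and stays controlled, the definition in 11.2 keeps the clock running. If the later therapy works, the recorded DOR is lengthened, in leflunomide's favour. An analyst who wants to separate the two periods needs the start date of the later therapy, and no follow-up visit is scheduled to collect it.

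This concerns the period off leflunomide and DOR only, not therapy given alongside leflunomide.

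**Working it through.** **The plan's own figures.** The documents state no DOR assumption or switching rate, so there is no DOR figure to reproduce. The precision figures in 12.2 do reproduce: for 5 responders of 12, the Clopper-Pearson limits are 15.2% to 72.3%, a width of 57.2 points against the stated 57%. The 4-, 5- and 6-responder scenarios in 12.2 (33%, 42%, 50%) give the number of responders on which DOR might rest.

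**What can happen under the text.** Suppose first response at month 1 (Cycle 2 Day 1), treatment stopped at month 3, another therapy started then, and no progression through the 12 months of follow-up. Follow-up ends at month 3 + 12 = 15. Recorded DOR is at least 15 − 1 = 14 months, of which 3 − 1 = 2 precede the new therapy.

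**Five responders (assumed data).** Three progress 3, 6 and 12 months after first response. Two follow the pattern above: switch at 2 months, progression-free at 14. The Kaplan-Meier estimate multiplies (1 − events/at risk) over event times.

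| Handling of the two switchers | Estimate at successive event times | Median |
|---|---|---|
| As written (censored at 14) | month 3: 4/5 = 0.80; month 6: 0.80 × 3/4 = 0.60; month 12: 0.60 × 2/3 = 0.40 | 12 months |
| Censored at the switch | month 3: 2/3 = 0.67; month 6: 0.67 × 1/2 = 0.33; month 12: 0 | 6 months |
| Switch counted as event | month 2: 3/5 = 0.60; month 3: 0.60 × 2/3 = 0.40; month 6: 0.20; month 12: 0 | 3 months |

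Censoring at the last assessment before the switch gives the same second row, since no progression occurs before month 3.

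**Six responders (assumed data).** Three progress at 3, 6 and 9 months; three switch at 2 and are progression-free at 14. As written: 0.83, 0.67, 0.50, median 9 (first time the estimate is at or below 0.5). Censored at the switch: 0.67, 0.33, 0, median 6. Counted as events: 3/6 = 0.50 at month 2, median 2. The 12-month estimate is 50% as written and 0% under either alternative.

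**How many switchers it takes.** Let *n* responders include *k* who switch before anyone progresses and stay progression-free past the median. With the same median convention, the median falls at progression number ⌈n/2⌉ as written and ⌈(n − k)/2⌉ when censored.

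| n, k | As written | Censored |
|---|---|---|
| 4, 1 | 2nd | 2nd |
| 5, 1 | 3rd | 2nd |
| 6, 1 | 3rd | 3rd |
| 4, 2 | 2nd | 1st |
| 5, 2 | 3rd | 2nd |
| 6, 2 | 3rd | 2nd |

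One switcher among four or six leaves the median where it was; one among five can move it by one progression time. When progressions may also precede the switch, shifts are rarer. In a simulation with exponential DOR (median 6 to 18 months) and a switch at 3 months, one switcher among five left the median unchanged in 63–77% of runs, with finite shifts typically of 2–4 months. Two among four or five left it unchanged in 31–65%.

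**Late switching (assumed model).** Exponential DOR with median 6 to 18 months; 25% or 50% of those still in response at month 12 switch; hazard ratio on the new therapy 0.5 or 0.25. The share in response at 18 months rises by about 1 point (12.6% to 13.9%) to 5 points (35.3% to 40.5%). At 23 months the rise is about 1.5 points (7.1% to 8.6%) to 8 points (26.5% to 34.5%). The median moves only where the true median lies beyond the switch: 18 months becomes about 19 to 22.

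**The case against.** Several stronger readings are tempting, and the documents do not support them.

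- *That switchers must stay in follow-up.* The reasons in 5.8 are not exhaustive and include investigator discretion, so a switcher could be taken off study. That would be case by case, and no DOR rule follows from it.
- *That the protocol expects responders to switch.* The discussion of alternative care in 5.6 and the window in Table 14.3 apply to everyone who stops treatment, including patients who have progressed and whose DOR has ended. They show that new therapy is foreseeable, not that responders are expected to start it before progression.
- *That the start date would be lost for good.* This is a single-centre study with source records. Section 5.9.1 asks that added therapy be recorded, though in a section mainly about treatment. Table 13.3 lists follow-up forms whose fields are not shown, and the Table 14.3 window requires knowing of new therapy for up to 90 days. An empty calendar cell is also weak proof of non-collection: biopsy at progression is required, yet its Active Follow-Up cell is empty too. What stands is that systematic capture is not scheduled.
- *That one switcher typically moves the median by many months.* The check above does not bear this out.

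Two further points have weight. Counting disease control regardless of later therapy is a legitimate estimand, and censoring at new therapy may be informative. Both argue for stating the choice in advance and showing the alternatives. Neither argues for leaving the rule unstated and the therapy unscheduled for recording.

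**Conclusion.** The point holds in a limited form. Applied as written, 11.2 and 12.4 can count disease control on a later therapy as leflunomide's DOR, and the calendar does not schedule collection of the date needed to separate the two. It affects one descriptive secondary endpoint in a pilot of 12 evaluable patients. Overall and complete response rates count only responses during study treatment and are not touched.

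The size cannot be known from the documents. On assumed data it ranges from nothing (one switcher among four or six responders) to a doubled median (12 against 6 months, two early switchers among five). Late switching adds about 1 to 5 points at 18 months. These figures rest on invented event times or an exponential model, and on the switchers staying controlled on the later therapy. The change should be made; it is not a flaw in the primary analysis.

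**What to change.** 1. Add type and start date of any new lymphoma-directed therapy (systemic, radiation, phototherapy, skin-directed) to the Active Follow-Up column of Table 10 and to the follow-up form.
2. In 11.2 and 12.4, state that DOR is censored at the last response assessment before the first such therapy.
3. Pre-state two sensitivity analyses, because that censoring may be informative: one counting the start of new therapy as an event, and one ignoring it, which is the current definition.

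The cost is one field at visits already planned every 3 months (12/3 = 4 per patient, so at most 14 × 4 = 56 entries) and a few sentences of text. The change restricts nobody's care. The downside is that DOR may come out shorter or more heavily censored, and with few responders the median may not be estimable.
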